1.4 Benefit/risk and ethical assessment

1.4.1 Individual benefit

There is no individual benefit to the patients included in the study.

1.4.2 Collective benefit

The extensive clinical experience with radiolabeled girentuximab has provided strong clinical evidence to support its use as a targeted PET imaging agent in clear-cell renal cell cancer.

CAIX, is a cell surface antigen expressed in 70% to 90% of bladder cancer NMIBC but not in normal urothelial tissue; therefore, it represents an optimal therapeutic target. There may be a role for CAIX as an intravesical target for instillation therapy(8).

Once ^{89}Zr -Girentuximab has been shown to be safe, we will develop a treatment of bladder cancer NMIBC for therapeutic purposes with girentuximab radiolabeled with a therapeutic radionuclide such as: $^{211}\text{Astatine}$.

Especially as local treatments such as mitomycin C and BCG therapy are in short supply worldwide, it is important to offer alternative treatments to postpone cystectomy.

1.4.3 Overall risks

In previous clinical studies, intravenous administration of Zirconium-89 (^{89}Zr) labeled monoclonal antibodies was proven to be safe (18,22).

Although never observed in previous trials, allergic-type reactions are possible during and immediately following the intravenous administration of girentuximab. In a total of more than 2000

intravenous administrations of radiolabelled murine and chimeric girentuximab to humans, no allergic-type reaction was observed.

Moreover, it has been clearly shown that, after an intravesical instillation, a radiolabelled antibody remains confined in the bladder without extravasation in the general circulation (6,7) making an allergic reaction unlikely. No toxicities have been reported in these two studies.

In PERTINENCE study, even if **no toxicity related to intravesical ^{89}Zr -Girentuximab administration is expected**, patients will be carefully monitored after intravesical ^{89}Zr -Girentuximab administration.

Some adverse events related to intravesical administration are expected: mictorial burning, deposition or scaling in the urine, pollakiuria, fatigue, fever and haematuria. Patient will be informed to contact the investigator if one of these adverse events occurs.

1.4.4 Benefit / risk balance

There is more than 20 years of experience in humans with SPECT/CT imaging using girentuximab labelled with various radioligands including ^{124}I and ^{111}In . These studies investigated the pharmacokinetics, toxicity, immunogenicity, and imaging characteristics of radiolabelled girentuximab in kidney cancer patients.

In a clinical phase 1 study investigating safety, tolerability, imaging characteristics, biodistribution and dosimetry, ^{89}Zr -TLX250 was found to be safe, and to provide improved imaging characteristics, compared to ^{124}I -girentuximab, in line with preclinical findings (15). The clinical development of ^{89}Zr -Girentuximab has found the optimal dose of radioactivity to $37 \text{ MBq} \pm 10\%$ of ^{89}Zr with a total dose of girentuximab of 10 mg.

The current PERTINENCE clinical trial will consist in intracavitory (intravesical) instillation of the same radiopharmaceutical " ^{89}Zr -girentuximab" used in the Telix phase 3 ZIRCON clinical trial with systemic intravenous injection and using the same activity (37 MBq).

With regard to the potential toxicity following this administration route, we refer to two previous preclinical and clinical studies performed with a different antibody, namely anti-Epidermal Growth Factor Receptor (EGFR) labeled with bismuth-213, an alpha-emitting radionuclide.

In a preclinical study with an orthotopic human bladder carcinoma mouse model, an activity of up to 0,925 MBq was intravesically instilled (7). Excellent retention of the therapeutic radiopharmaceutical in the bladder with negligible systemic activity was observed.

It is important to note that no macroscopic urothelial lesions caused by a-particle irradiation was observed.

In a subsequent clinical pilot study, an activity of up to 821 MBq (22mCi) of the same radiopharmaceutical was intravesically instilled in 12 patients (6).

It was clearly shown that ^{213}Bi activity remained in the bladder with no systemic uptake and reflux into the ureters as observed in the preclinical study (Figure 9).

[figure not shown]

Figure 9: Distribution of ^{213}Bi -anti-EGFR MAb after intravesical instillation visualized via SPECT/CT imaging: all activity remains in the urinary bladder.

All 12 patients treated with the ^{213}Bi -immunoconjugate showed excellent tolerance without any signs of adverse effects. ^{213}Bi was not detected in blood samples taken from patients during 1 to 2 hours after treatment.

Overall, no toxicity at all was observed in both preclinical and clinical studies.

The antibody used in the PERTINENCE study is different but the same retention inside the bladder should be expected due to the size of the antibody molecule.

The radionuclide also is different but a higher toxicity could be expected with alpha-emitting bismuth-213 radionuclide than with positron-emitting zirconium-89 due to a much higher Linear Energy Transfer (LET).

Consequently, no toxicity at all is expected in the PERTINENCE study after intravesical instillation of 37 MBq of ^{89}Zr -girentuximab.

According to the information described above, it appears that the benefit/risk ratio will be clearly in favour of the benefit to the patient.

The results of Pertinence study may contribute to the development of a new targeted therapy for Non-Muscle-Invasive Bladder Cancer (NMIBC) with girentuximab labelled with a therapeutic radionuclide such as astatine-211 (^{211}At -Girentuximab).

2. OBJECTIVES

2.1 Primary objective(s) and endpoint

2.1.1 Primary objective

The primary objective of this study is to assess the biodistribution of ^{89}Zr -girentuximab.

2.1.2 Endpoints of primary objective

- ⇒ Bladder uptake will be evaluated quantitatively using SUVmax, SUVmean and (Bq/ml) at different time points (T0, T0+2h, T0+20h and T0+44h)
- ⇒ The activity retained by the bladder at T0 will be assessed by the difference between the instilled activity (Bq) and the activity after rinsing measured in the saline solution used for rinsing (Bq).
- ⇒ Biodistribution in whole body will be assessed visually and quantitatively by PET/CT imaging of whole body at T0+2H and quantitatively by assessing the ^{89}Zr -Girentuximab activity in blood at T0+20h. Another PET/CT imaging of whole body will be performed at T0+44h in case of positive blood radioactivity at T0+20h.

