- **T0:** At the end of ⁸⁹Zr-TLX250 administration: 2 hours after intravesical instillation, a first imaging session centred on the **bladder** will be performed (with full bladder) and will allow to evaluate the possibility to identify the ⁸⁹Zr girentuximab uptake surface and to measure tumor and normal bladder wall surface. Spatial distribution of PET/CT images will cover the lone bladder. PET acquisition duration will be adjusted to allow a sufficient count statistics for a good quality of activity measurements in main organs.
- **T0 + 2 hours:** a **whole body scan** will be performed (with empty bladder), from the skull base to the mid-thigh, to ensure that no residue ⁸⁹Zr-TLX250 pharmaceutical occurred outside the bladder and spread in the rest of the body. During the whole body scan, the specific step including the bladder will be designed.
- **T0 + 20 hours (day 1):** a new imaging session centred on the **bladder** will be performed (same protocol as first session) in order to quantify the remaining activity and calculate the decay of the later. The aim is to check that there is no residual radiopharmaceutical outside the bladder through the urethra.

On day 1, a blood sample will be drawn in order to check the absence of activity from residual ⁸⁹Zr-TLX250 in blood.

- **T0 + 44 hours (day 2):**
 - ⇒ If blood radioactivity testing on day 1 is **negative**, a **bladder scan** should be performed on day 2 (T0 + 44 hours).
 - ⇒ If blood radioactivity testing on day 1 is **positive**, a **Whole body scan** should be performed on day 2 (T0 + 44 hours). This scan will permit to localise the uptake of the residual pharmaceutical.

In total, 4 imaging sessions will be performed, including a whole body scan and in case of residual activity in the day 1 blood sample, a second whole body scan will replace the bladder centred scan.

PET studies will be performed with a PET/CT hybrid system. A CT acquisition will be coupled to a PET acquisition for attenuation correction and anatomical tracking.

Low-dose CT acquisition parameters will be those usually used namely:

- Field: several fields of view allowing visualization of the bladder and whole body.
- Number: four acquisition times:
- Time 0: 2 hours after instillation:
 - Full bladder imaging: one step centred on the bladder after CT acquisition of the step.
- ⇒ Time 1: 4 hours after instillation:

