4.2.3.2 Semiquantitative ^{89}Zr -TLX250 Tumor Targeting

SUVs will be calculated for the tumor bladder lesion, considering the measured tumor-bound activity, the injected activity dose, and the body weight and height of each patient.

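### Primary endpoint 1 follows bladder uptake by concentration alone and names no region; a whole-bladder mean would mix bladder volume with retained activity between the full T0 scan and the empty T0+2h scan

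*Combined protocol and SAP*

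**What the plan says.** The first primary endpoint in section 2.1.2 reads: "Bladder uptake will be evaluated quantitatively using SUVmax, SUVmean and (Bq/ml) at different time points (T0, T0+2h, T0+20h and T0+44h". Section 9.2.2 (Monitoring Plan) repeats it. Neither place says whether the region is the whole bladder, its wall, its lumen or the lesion.

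Two other sections bear on the region. Section 4.2.3.2, on tumour targeting, says "SUVs will be calculated for the tumor bladder lesion"; it does not mention Bq/ml or the primary endpoint. Section 4.2.2 says the T0 scan also serves "to measure tumor and normal bladder wall surface".

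Section 4.2.2 sets the filling state scan by scan:
- T0: the session "will be performed (with full bladder) and will allow to evaluate the possibility" of identifying the uptake surface.
- T0+2h: the whole-body scan "will be performed (with empty bladder), from the skull base to the mid-thigh". Its stated purpose is to look for tracer outside the bladder.
- T0+20h: "same protocol as first session) in order to quantify the remaining activity and calculate the decay of the later".
- T0+44h: no filling state appears in the supplied text.

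The second primary endpoint is an amount in Bq, but at one time only: "The activity retained by the bladder at T0 will be assessed by the difference between the instilled activity (Bq") and the activity measured in the rinse.

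**The concern.** The protocol wants an amount. Section 4.2.2 wants the activity remaining at T0+20h, section 4.2.3.1 wants to show that activity stays in the bladder, and section 4.6 says that any late leakage will be studied by quantified bladder imaging. A concentration gives an amount only when multiplied by a volume, and the endpoint includes no volume.

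The gap matters most between T0 and T0+2h, where the protocol itself changes the bladder from full to empty within one primary-endpoint series. If the reader of the images draws the whole bladder, the mean can move because the bladder has shrunk. A rise could then be read as retention or uptake when total activity has fallen.

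Because the region is open, two analysts could measure different things and both comply with section 2.1.2. With 6 patients and descriptive summaries only, each patient's series is the result, and no control group or test would expose a misreading.

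**Working it through.** **The plan's own figure.** There is none to reproduce. The sample size of 6 rests on no alpha, power, effect size or SD, and the point does not depend on it.

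**Inputs from the documents.** Filling states are from section 4.2.2. The 89Zr half-life is about 3.3 days = 79.2 h (section 1.2.3.1.3).

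**Assumed inputs.** Full lumen V1 = 200, 300 or 400 ml; empty lumen V2 = 50 or 100 ml; wall W = 30 or 60 ml. Let b be the share of T0 activity bound to the wall, with none of the bound tracer lost by T0+2h.

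**Formulas, whole-bladder region, decay-corrected, T0+2h divided by T0.**
- Volume factor F = (V1 + W)/(V2 + W).
- Total ratio R = b + (1 − b)·k. Here k = V2/V1 if urine concentration is unchanged on voiding, and k = 0 if luminal tracer is fully cleared.
- Mean ratio = R × F.

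**Volume factor.** Smallest: (200 + 60)/(100 + 60) = 260/160 = 1.625. Largest: (400 + 30)/(50 + 30) = 430/80 = 5.375.

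| Bound share b | Luminal tracer at T0+2h | Total ratio | Mean ratio |
|---|---|---|---|
| 1 | none to clear | 1.00 | 1.625 to 5.375 |
| 0.5 | same concentration | 0.75 to 0.5625 | 0.75 × 1.625 = 1.22 to 0.5625 × 5.375 = 3.02 |
| 0.5 | fully cleared | 0.50 | 0.5 × 1.625 = 0.81 to 0.5 × 5.375 = 2.69 |

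With half bound, total activity therefore falls 25% to 50%, while the mean ratio lies anywhere from 0.81 to 3.02.

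**Bound share above which the mean rises.**
- Unchanged urine concentration: W/(V1 + W), from 30/430 = 7% to 60/260 = 23%.
- Full clearance: (V2 + W)/(V1 + W), from 80/430 = 19% to 160/260 = 62%.

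**Sensitivity to the assumed volumes.** With 150–400 ml full, 20–100 ml empty and the same wall, F runs from 210/160 = 1.3 to 430/50 = 8.6. If urine activity at T0 is half the wall activity and 90% of it clears, the total ratio is 1.05/1.5 = 0.70 and the mean ratio runs from 0.92 to 6.0.

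**Physical decay.** 0.5^(2/79.2) = 0.983, 0.5^(20/79.2) = 0.839 and 0.5^(44/79.2) = 0.680. Decay over 2 h is too small to explain shifts of this size. Uncorrected Bq/ml would fall 16% over 20 h and 32% over 44 h from decay alone, and section 2.1.2 does not say whether it is corrected.

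**Total activity instead.** Mean Bq/ml × segmented volume returns R itself. It is 1.00 when nothing is lost, whatever the filling.

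**The case against.** The strongest reply is that the only SUV region the documents name is the tumour lesion, and that the T0 scan is also meant for tumour and wall surface. For a lesion or wall region the luminal volume largely drops out, and SUVmax is not an average over the region. This stands, and it is why the point is conditional. It does not close the gap: section 4.2.3.2 is silent on Bq/ml and on the primary endpoint, and a lesion value would describe the lesion, not the bladder.

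Second, no change from T0 to T0+2h is an endpoint, and the protocol's own retention comparison is T0+20h, scanned as at T0. This also stands. The harm is a misread series, not a wrong test. But section 2.1.2 does list T0+2h as a bladder-uptake time.

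Third, quantification is already intended, and volumes could be segmented later from the stored CT. True, so no data would be lost; the intent is simply not carried into the endpoint.

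Fourth, total activity is not uptake either. In the half-bound case it falls 25–50% with no loss of bound tracer. Section 4.2.1 describes measuring urine activity only around the post-instillation rinse, so it cannot be set beside the later scans. This stands and limits what the fix can claim.

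A reader might infer that the mean must rise on voiding and so always overstates retention. The documents do not support that. Sections 4.2.1 and 4.6 have patients drinking and voiding, so luminal tracer may be diluted or cleared, and the ratio can then fall below 1. Nor is a missing T0+44h filling state established: Appendix 7, on the instillation procedure, is listed but not in the supplied text and may state it.

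**Conclusion.** The point holds in a limited form. Endpoint 1 names no region, relies on concentration alone, and puts a full-bladder and an empty-bladder scan in one series. If the region is the whole bladder, SUVmean and mean Bq/ml at T0 and T0+2h depend on volume as well as activity.

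That some volume effect exists follows from the filling states in section 4.2.2. Its size rests entirely on assumed volumes, and with only part of the activity bound its direction also depends on luminal clearance.

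The documents do not support a claim that the whole series is unusable: T0 and T0+20h share a protocol and are nominally comparable, although the filling volume is not fixed. What does follow is that the concentration series alone cannot show the remaining activity that sections 4.2.2 and 4.6 want, and the Bq endpoint covers T0 only. The change should be made because it is cheap and supplies the quantity sought.

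**What to change.** In sections 2.1.2 and 9.2.2:
1. State the region (whole bladder, wall or lesion) for each of SUVmax, SUVmean and Bq/ml, and reconcile it with section 4.2.3.2.
2. Add a descriptive per-patient measure at every scan: total activity in a segmented whole-bladder volume (mean Bq/ml × volume), decay-corrected to instillation, in Bq and as a percentage of instilled activity. Use recorded clock times, because section 4.2.2 labels the day 1 scan both T0+20h and 20 hours after instillation, while T0 is itself 2 hours after instillation.
3. Record segmented volume and filling state at each scan, including T0+44h whether it is a bladder or a whole-body scan.
4. Compare whole-bladder SUVmean and mean Bq/ml only between scans at the same filling state. SUVmax and lesion SUVs can stay as planned.
5. State that the total includes luminal tracer and so falls with voiding, and that a lesion or wall measure is needed to describe binding. List the urine activity of section 4.2.1 beside the total at T0 only, with no new urine collection.

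Cost: endpoint wording and 4 segmentations × 6 patients = 24. No extra scan is needed, since "A CT acquisition will be coupled to a PET acquisition for attenuation correction and anatomical tracking". The drawback is a total that does not by itself separate voiding from loss of binding.

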1.3 Rationale for conducting this study

⁸⁹Zr-Girentuximab is under clinical development as a PET/CT imaging radiopharmaceutical for the detection of renal tumor masses and metastases (which overexpress CAIX). When the anti-CAIX antibody, girentuximab is labelled with a PET radionuclide such as ⁸⁹Zirconium, it can be used as an imaging probe for PET.

CAIX has recently emerged as a very attractive therapeutic target due to the following features:

- ⇒ CAIX is expressed in several cancers. Especially, it is expressed in 70% to 90% of bladder cancers but not in normal urothelial tissue (8).
- ⇒ CAIX is expressed on the membrane of Non-Muscle-Invasive Bladder Cancer cells (8,21).

Klatte et al. showed that CAIX has a role as a diagnostic, prognostic, and therapeutic molecular marker. Because CAIX expression and is highly expressed in noninvasive, low-grade bladder cancer, the evaluation of CAIX may be a useful adjunct to diagnostic cytology, and intravesical CAIX targeted therapy may be effective in these high CAIX-expressing tumors. Likewise, because metastatic tumors express high CAIX, an evaluation of systemic CAIX-targeted therapy as a therapeutic approach is warranted (8).

The current project will consist of an intravesical instillation of anti-CAIX antibody (girentuximab) labeled with an activity of 37 MBq of positron-emitting zirconium-89.

In previous clinical studies, intravenous administration of Zirconium-89 (⁸⁹Zr) labeled monoclonal antibodies was proven to be safe.

Furthermore, it has been clearly shown that, after an intravesical instillation, a radiolabeled antibody remains confined in the bladder without extravasation in the general circulation (6,7). Thus radiation is limited to the bladder wall. In the clinical pilot study performed with an antibody

labeled with an activity of up to 740 MBq of an alpha-emitting radionuclide (bismuth-213) much more irradiating than zirconium-89 no toxicity at all has been observed. Thus no toxicity is expected in the current proposal consisting in an instillation of 37 MBq of zirconium-89 followed two hours later by a lavage of the bladder.

One of the objectives of this study is to assess the biodistribution of ^{89}Zr -girentuximab in whole body if it exists.

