4.2.1 Dosage and Administration

This is sufficient to draw up the patient dose of 37 MBq of ⁸⁹Zr- TLX250, adjusted to 10 mg of girentuximab at the time of injection.

The study medication will be prepared as individual syringe in ICO radiopharmacy by a dedicated pharmacist within one hour of administration.

The investigator should check that the urine cytobacteriological testing is negative before intravesical instillation to ensure the absence of germs.

The ⁸⁹Zr-Girentuximab solution (about 10 ml) will be administered into the emptied bladder through a urethral catheter using natural urinary tract (see intravesical instillation procedure in appendix 7).

The syringe will be washed with 30 ml of saline solution which will be also injected into the bladder. The urethral catheter should be removed.

Patients will be asked to turn over repeatedly to ensure equal distribution of ⁸⁹Zr-Girentuximab in the bladder.

The ⁸⁹Zr-Girentuximab should be maintained in the bladder for no more than 1.5 hours: duration of ⁸⁹Zr-Girentuximab administration.

Then, the patient will be asked to drink water and urinate to rinse the bladder, the patient will drink water again and the first PET/CT imaging centered on the bladder will be performed about 2 hours after instillation.

The urethral catheter and the urine activity will be measured.

A whole body imaging should be performed 2 hours after ⁸⁹Zr-Girentuximab administration (4 hours after instillation) (see intravesical instillation procedure in appendix 7).

The investigator or his/her designee will administer the study drug to the subjects, exercising accepted medical practices. Under no circumstances will the investigator allow study drugs to be used otherwise than as directed by this clinical study protocol. Study drug administration will be done under direct medical supervision.

4.2.2 ⁸⁹Zr-TLX250 PET/CT Imaging

Imaging sessions are necessary to check the safety of intravesical application of ⁸⁹Zr-TLX250 pharmaceuticals. Two aspects will be studied:

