7.1.3 Expected adverse events

An Expected adverse event (EAE) is an effect already mentioned in the most current version of the applicable document used in this trial.

Reminder: Expected serious adverse events will be submitted by the sponsor to the competent authorities.

In PERTINENCE study, **we don't expect any ⁸⁹Zr-girentuximab adverse event** as it will be administered intravesically and rinsed out afterwards. It will not diffuse into the general circulation as with intravenous administration.

Clinical experience in 69 patients dosed with a **single intravenous administration** of ⁸⁹Zr-girentuximab exhibited that less than 10% of patients experienced a mild nausea, which was considered related to the study medication. Therefore, mild nausea is an expected side effect of girentuximab in case of single intravenous administration.

Expected adverse events related to intravesical administration are: mictorial burning, deposition or scaling in the urine, pollakiuria, fatigue, fever and haematuria. Patient will be informed to contact the investigator if one of these adverse events occurs.

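### The primary endpoint for bladder-retained activity at T0 subtracts a saline rinse that Section 4.2.1 does not describe and omits the urine and catheter activity that it measures

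*Combined protocol and SAP*

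**What the plan says.** Section 2.1.2 lists three primary endpoint items. The second is the activity the bladder retains at T0, taken as instilled activity minus the "activity after rinsing measured in the saline solution used for rinsing (Bq"). Section 9.2.2 repeats this definition among the items that monitors must verify.

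Section 4.2.1 describes the procedure:

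- Saline appears once: "The syringe will be washed with 30 ml of saline solution which will be also injected into the bladder". The catheter is then removed.
- The product stays in the bladder for at most 1.5 hours. "Then, the patient will be asked to drink water and urinate to rinse the bladder".
- "The urethral catheter and the urine activity will be measured".
- The dose is "prepared as individual syringe in ICO radiopharmacy by a dedicated pharmacist within one hour of administration".

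Other sections describe the emptying differently. Section 1.3 has the instillation "followed two hours later by a lavage of the bladder", without naming the fluid. Section 7.1.3 justifies expecting no drug-related events "as it will be administered intravesically and rinsed out afterwards". Section 4.2.1 refers to Appendix 7 for the full instillation procedure; the appendix is listed, but its text is not in the public documents.

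**The concern.** The endpoint names a fluid that 4.2.1 does not recover and leaves out both quantities that 4.2.1 measures. The saline in 4.2.1 enters the bladder with the dose, so it belongs to the input side of the balance. The formula also gives no decay reference time and does not say whether instilled activity is net of what stays in the syringe.

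Site staff would have to improvise. If they use urine alone in place of the saline, catheter residue and any uncorrected decay are counted as activity held by the bladder. The quantity is a small difference between two large activities, so small omitted terms can dominate it. With six patients and descriptive summaries only (Sections 8.1 and 8.4), a systematic error does not average out, and improvised choices could differ between patients.

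**Working it through.** The plan gives no figure for this endpoint to reproduce, so the check is a mass balance.

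**Inputs**

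- Instilled activity: 37 MBq ± 10% (Section 4.1.2).
- Half-life of ⁸⁹Zr: about 3.3 days (Section 1.2.3.1.3), so 3.3 × 24 = 79.2 h.
- Fraction remaining in the bladder: one tenth or one hundredth (Section 4.6). This gives 3.7 or 0.37 MBq retained, and 33.3 or 36.63 MBq recovered.
- Times: at most 1.5 h retention and up to 1 h between syringe preparation and administration (4.2.1); T0 is 2 h after instillation (4.2.2).

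**1. Literal reading.** If no saline is recovered, the subtracted term is missing or zero. Taken as zero, the endpoint is 37 − 0 = 37 MBq, or 100% retained, whatever the truth. Against 3.7 and 0.37 MBq this is too high by factors of 10 and 100. The factors are the same at 33.3 and 40.7 MBq.

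**2. Urine substituted, no decay correction.** Let t run from the assay of the instilled activity to the assay of the recovered fluid, and take the second assay as the reference time. The excess counted as retained is 37 × (1 − 2^(−t/79.2)).

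| t | Origin | Decay | Excess (MBq) | Relative to 3.7 MBq | Relative to 0.37 MBq |
|---|---|---|---|---|---|
| 1.5 h | maximum retention | 1.30% | 0.48 | 13% | 130% |
| 2 h | instillation to T0 | 1.74% | 0.64 | 17% | 174% |
| 3 h | syringe assayed at preparation, 1 h earlier | 2.59% | 0.96 | 26% | 259% |

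**3. Catheter left out.** The documents give no residue. Each assumed 1% of the dose left in the catheter adds 0.01 × 37 = 0.37 MBq, which is 10% of 3.7 MBq or 100% of 0.37 MBq. The effect scales in proportion.

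**4. Incomplete collection.** If a share s of the outflow is counted and a fraction f is truly retained, the endpoint reads 1 − s(1 − f). With s = 0.9 (assumed), 10% reads as 1 − 0.9 × 0.90 = 19%, and 1% reads as 1 − 0.9 × 0.99 = 10.9%. With s = 0.95 the readings are 14.5% and 5.95%.

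**5. What remains after correction.** With every term included, complete recovery and one reference time, the formula returns 37 − 33.3 = 3.7 MBq or 37 − 36.63 = 0.37 MBq. An assumed 1% error in the recovered activity is still 0.33 MBq (9% of 3.7) or 0.37 MBq (99% of 0.37). At the low end the endpoint is therefore imprecise even when properly defined.

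**The case against.** The strongest reply is that Appendix 7 holds the detailed procedure and may describe a recovered saline rinse. That is possible, and the public text cannot settle it. It would not remove the conflict: if the appendix has such a rinse, 4.2.1 is incomplete; if it has none, the endpoint names the wrong fluid.

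A second reply is that the saline simply means the voided fluid. The bladder holds about 10 ml of product plus 30 ml of saline, and Section 4.6 links excretion to the rinsing stage. This is a plausible intention, though the text does not state it. It would still leave the catheter, the collection window and the decay reference undefined.

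Several points limit the size:

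- The plan does not exclude decay correction.
- The range of one tenth to one hundredth comes from a dose-rate illustration for radiation protection, not from a retention estimate for this endpoint.
- If activity is referred to the time of instillation, only the recovered part carries the decay error. At one tenth retained, 33.3 MBq × 1.30%, 1.74% and 2.59% gives 0.43, 0.58 and 0.86 MBq, or 11.7%, 15.6% and 23.3% of 3.7 MBq. The larger figures in the table suit an endpoint defined at T0.
- The saline wash will reduce syringe residue.

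Finally, this is a six-patient exploratory study in which no test or decision threshold uses the quantity. That bears on severity; it does not make the formula computable.

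**Conclusion.** The concern holds. One of the three primary endpoint items cannot be computed as written from the procedure in 4.2.1, and it omits the two measurements which that section provides. It should be fixed.

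The size depends on what staff do in place of the missing rinse. Substituting urine without decay correction adds 0.48 to 0.96 MBq. That is 13% to 26% of the result if one tenth of 37 MBq remains, and more than the whole result if one hundredth remains. These figures rest on the stated half-life, the Section 4.6 range and the absence of any correction. The catheter, collection and assay figures are assumptions. The PET uptake, whole-body and blood items do not use this formula and are not affected.

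**What to change.** In Sections 2.1.2 and 9.2.2, define:

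retained activity at T0 = net instilled activity (syringe activity before instillation minus syringe residue) − catheter activity − activity in all urine or rinse fluid recovered between instillation and the T0 scan,

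with assay times recorded and every term decay-corrected to T0. State that the result is activity not recovered, so it also includes unbound activity still in the bladder and any absorbed activity. Report its measurement uncertainty.

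Reconcile Sections 1.3, 2.1.2, 4.2.1, 7.1.3 and 9.2.2 and Appendix 7 on what the rinse consists of and when it occurs. Which procedure applies is for the sponsor to settle.

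Optionally, report total bladder activity on the T0 PET beside the result as a mass-balance check. Section 4.2.2 says that this session "will be performed (with full bladder) and will allow to evaluate the possibility" of identifying the uptake surface; because the bladder is full after further drinking, the total includes unbound activity in urine. The T0+2 h scan, planned with an empty bladder, can be shown as the image with less urine activity.

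The cost is wording in two sections plus the reconciliation. Urine and catheter measurements are already planned. The additions are one residual-syringe reading, recorded assay times and complete collection of urine or rinse fluid up to T0; the optional PET comparison would add a small analysis.
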